**Figure 4: Overall Study Design**

BSC = best supportive care; DMC = Data Monitoring Committee; ICF = informed consent form; Q3W = every 3 weeks; SC = subcutaneous; UNBL = unblinding; LPFD = last patient first dose.

a The historical documentation of transfusion dependence for  $\beta$ -thalassemia subjects (including units transfused and hemoglobin (Hb) levels measured prior to each transfusion) for 24 weeks prior to subject randomization, should be available.

b Dose may be titrated up to a maximum of 1.25 mg/kg.

c Randomization will be 2:1, luspatercept plus BSC versus placebo plus BSC.

d All subjects, who complete 48 weeks of the double-blind Treatment Period of this study will have the opportunity to continue to a double-blind Long-Term Treatment Period at the Investigator's discretion. Subjects who do not enroll in the double-blind Long-Term Treatment Period or who discontinue early will proceed to the Post-treatment Follow-up Period.

[figure not shown]
e Maximum duration of 48 weeks post LPFD, or when all subjects completed 48 weeks of double-blind treatment or discontinued before reaching 48 weeks double-blind treatment, or in the event the study is unblinded per DMC recommendation.

f Open-label Phase: Subjects who were compliant with the protocol 48 weeks post Dose 1 Day 1 can enter in the Open-label Phase, unless medically contraindicated and as described in Section 3.1.4.

g Early discontinued subjects, ie, subjects who discontinue before completing the double-blind treatment period (48 weeks), will continue to be monitored on week 9, followed by 24, 48, 72, 120, 144 after the last dose up to Week 156, ie 3 years (refer to Section 3.1.5).

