**Table 3: Table of Events (Continued)**

Assessments	Section	Screening/ Run-in Period Week -12 to Day -1	Treatment Period (double-blinded)				Long-term Treatment Period  (double- blinded) every 3-wk visits from Week 49 (ie, Dose 17 if no dose delays) /Day 1 (± 5 days)	Open-label Phase, every 3-wk visits from unblinding (± 5 days)		Day 22 Post Last Dose/ Treatment D/C 	Post-treatment Follow-up Period (± 7 days)			
			Luspatercept/ placebo Dose 1 Schedule (+7 days)		Luspatercept/placebo Doses 2 up to max 48 weeks Treatment (± 3 days)			Dose 1 for Placebo, Discont. 	Dose X Day 1 		Follow- up Week 9 (from last dose) 	Only if  Early Discont. – Follow-up Visits weeks 24, 48, 72, 96, 120, 144 (from last dose) 	All subjects: Follow- Up Visits weeks 24, 48, 72, 96, 120, 144 (from last dose) 	End of Study  / Follow- up week 156 (from last dose) 
			Day 1	Day 1	Day 8	Day 15								
Prior/concomitant/post procedures (eg, surgery, radiation therapy)	6.1 to 6.6	X	Record on ongoing basis, until 9 weeks Post-last Dose 											
Transfusion Assessment (≥ 24 weeks of history prior to Dose 1 Day 1)	6.1 to 6.6	X	Record on ongoing basis, until 9 weeks Post-last Dose 											
Subject Transfusion – information collection 	6.1 to 6.6	X	Record on ongoing basis, until 9 weeks Post-last Dose 											
Safety Assessments														
Adverse Events	6.1 to 6.7	Continuous starting after informed consent signature, until 9 weeks post last dose, related AE to be reported until End of Study												
Malignancy and Pre-malignancy Reporting (Section 10.5.2) 	6.1 to 6.7	Continuous starting after informed consent signature, regardless of causality reporting occurrence of any case									X 	X 	X 	
Vital Signs 	6.1 to 6.7	X (within 4 wks prior Dose 1 Day 1)	X	X	-	-	X	X	X	X	X			

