-  LTTP will end when all subjects completed 48 weeks of double-blind treatment or discontinued before reaching 48 weeks double-blind treatment, whichever is the earlier date, or at the time the study is unblinded (per DMC recommendation). Only subjects that do not discontinue for reasons as described in Section 11 can enter in the LTTP.
-  Only for subject who discontinue prior to completion of 48 weeks in the double-blind Treatment Period.
-  End of Study visit can occur at any time up to at least 156 weeks post last dose.
-  HCV-RNA test and HBsAg and/or HBVDNA .
-  +/- 10 day window around for MRI assessments and DXA is allowed (MRI for LIC, myocardial iron, spleen and LVEF). These assessments to be performed as indicated on specified week, regardless of dose delays. MRIs and DXA scans performed within the 4 weeks prior to the ICF signature can be accepted, if subject does not show any relevant clinical symptoms judged by the Investigator as sufficient reason to repeat these procedures within the Screening/Run-in period and agreed with the Sponsor.
-  Placebo subject who discontinued the study, but were compliant with the protocol 48 weeks post Dose 1 Day 1, and continued their participation in the Post-treatment Follow-up Period until the time of unblinding, refer to Section 3.1.4.
-  For all subjects on treatment at the time of Open-label Phase initiation, continue with the appropriate dose number.
-  For subjects who have documented diagnosis of  $\beta$ -thalassemia in their medical history, by other methodology or do not have a source laboratory report in the medical files, the  $\beta$ -thalassemia genotype can be done at any time during the course of the study.
-  The same Cardiac Doppler Echocardiography technique should be used within a subject throughout the study duration.
-  As per standard of care.
-  Follow-up visits at Weeks 9, 24, 48, 72, 96, 120, 144 and 156 post last dose should be performed by all subjects, regardless if a subject has Early Discontinued or not.
-  For early discontinuation subjects, these parameters to be reported up to 48 weeks Post Dose 1 Day 1 or Week 9 post last dose whichever is the later date.

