## 9.6. Efficacy Analysis

### 9.6.1. Primary Efficacy Analysis

The efficacy analysis will be performed on the ITT population. The primary efficacy analysis will be performed based on 24 weeks of data after all subjects have completed the double-blind 24-week treatment period phase or discontinued before reaching 24 weeks of double-blind treatment (for this study one month equal to 4 weeks is considered). A higher response rate in the luspatercept over placebo and a p-value < 0.05 will confirm the superiority of luspatercept in the efficacy.

The primary efficacy endpoint of this study is defined as subjects with  $\geq 33\%$  reduction from baseline in RBC transfusion burden with a reduction of at least 2 units from Week 13 to Week 24 compared to the 12-week interval prior to randomization for luspatercept plus BSC versus placebo plus BSC.

For the early discontinued subjects, ie, who did not complete 24 weeks of double-blinded treatment period, the transfusion records will still be collected up to 48 weeks. All the transfusion records will be used to evaluate primary and secondary endpoints.

The first day to be used for statistical analysis will be defined as the date of the first dose. A transfusion received on Dose 1 Day 1 will be counted in the baseline transfusion burden.

The primary endpoint response rate is calculated using the number of responders divided by all subjects in the ITT population. The response rates of the subjects who randomized to luspatercept and the placebo will be calculated. Let  $P_1$  denote the true response rate in the luspatercept group, and  $P_2$  denote the true response rate in the placebo group. In the primary efficacy analysis, the statistical hypothesis is

$$H_0 : P_1 = P_2$$

$$H_a : P_1 \neq P_2$$

The number and percentage of subjects in the ITT population who achieve the response will be calculated for luspatercept and placebo. The difference in proportions between luspatercept and placebo will be calculated and the Cochran Mantel-Haenszel (CMH) chi-square test would be performed using randomization factors as strata, corresponding 95% confidence interval (CI)

associated with the test will be provided. A higher response rate in the luspatercept arm over placebo arm with a p-value < 0.05 will infer that luspatercept is significantly superior to placebo.

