- All listings will display original collected values, cases with special marks (i.e., <500) will be listed as it is. The special mark will be removed if the value is used for calculation in tables.
- All analysis and summary tables will have the analysis population sample size (i.e., number of subjects) if not otherwise specified;
- All summary tables will be displayed by treatment (“Luspatercept + BSC” and “Placebo + BSC”), the “Total” group will be added for sections if specified;
- The day of the first dose of IP will be defined as Day 1; for erythroid response related endpoint, if a subject is not treated, the randomization date will be used as Day 1.
- In general, if not otherwise specified, baseline value will be defined as the last value (including “unscheduled”) on or before the date of the first dose of IP (if collecting time is available, date/time will be used to compare with first dosing date/time to identify baseline record, if there is no time available, only date will be used); if multiple values are present for the same date/time, the average of these values will be used as the baseline. For subjects who were not treated, the value on or prior to randomization date will be used. Specifically, for the laboratory hematology parameter ‘Leukocytes’, the baseline is defined as the highest value between screening visit and dose 1 day 1 visit.
- For data handling in change from baseline and shift tables (except for MRI and DXA parameters), “unscheduled” visits will be grouped with the closest scheduled visit based on assessment date. The average will be used as value for that scheduled visit in change from baseline tables; the worst category will be used in shift tables. If an unscheduled visit has equal distance to two scheduled visits, it will be grouped with the later visit. Specifically, for ADA titer summary, the titer value won’t be averaged if an “unscheduled” visit is mapped to the closest scheduled visit. The titer for “unscheduled” visit will only be used for summary if the original scheduled visit has no titer result.
- For RBC transfusion related efficacy endpoints summary, the 12-week interval before Week 48 is defined as:

Baseline 12-week interval: from Day -83 to Day 1;
Week 1 - 12 interval: from Day 2 to Day 85;
Week 13 - 24 interval: from Day 86 to Day 169;
Week 25 - 37 interval: from Day 170 to Day 253;
Week 37 - 48 interval: from Day 254 to Day 337.

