10. EFFICACY ANALYSIS

All efficacy evaluations are conducted using the ITT population, with the exception of Quality of Life analyses that are conducted on the HRQoL evaluable population. Statistical comparisons are made between luspatercept plus BSC vs. placebo plus BSC. Key secondary efficacy results are considered statistically significant after consideration of the strategy for controlling the family-wise Type 1 error rate, as described in Section 10.1, Multiplicity. All statistical tests are 2-sided at the significance level of $\alpha = 0.05$, and the corresponding p-values and 2-sided CIs for point estimates are reported, unless specified otherwise.

For the early treatment discontinued subjects, i.e., patients who did not complete 24 weeks or 48 weeks of double-blinded treatment period, the transfusion records were collected up to 48 weeks or 9 weeks post last dose, whichever was the later date. All the transfusion records collected throughout the entire study period up to the efficacy cutoff date were used in the RBC related efficacy analyses. The efficacy cutoff date for the primary CSR was defined as the minimum date among death date, study discontinuation date, last dose date + 20, and 11MAY2018. For the primary and key secondary endpoints, if at the time of data summary, a subject's efficacy cutoff date was before the end of the 12-week interval or a subject had any invalid transfusion records (i.e., transfusion unit not available) during the specified 12-week interval, this subject was included in the analysis as a non-responder.

All the efficacy analysis for the final CSR will not include the assessments for the placebo patients who crossed over to luspatercept. In other words, the assessments for the placebo patients will be analyzed up to the cross-over timepoint. For those subjects in the original luspatercept treatment, their assessments will be analyzed until the new efficacy cutoff date which is defined as the minimum date among death date, study discontinuation date, last dose date + 20.

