The OR (luspatercept versus placebo) with corresponding 2-sided (at 0.05 alpha level) 95% CI and p-value was provided. The difference in proportions (luspatercept – placebo) was also calculated. A forest plot showing the ORs, 95% CI and p-value for the overall result and the results in each subgroup was constructed for each endpoint.

The fourth secondary endpoint, mean change in RBC transfusion burden at the 12-week interval of Week 13 to Week 24 from the baseline 12-week interval, was analyzed using analysis of covariance (ANCOVA) with baseline values and geographical regions defined at randomization taken as covariates for the ITT population. Treatment effect was evaluated as a contrast of luspatercept versus placebo. Least squares (LS) means with corresponding standard errors (SE) for each treatment group, along with LS mean of treatment difference with corresponding 95% CI and p-value were presented. Also, summary statistics for RBC transfusion burden, change from baseline and percent change from baseline in RBC transfusion burden were provided by treatment group for the following 12-week intervals: Week 1 to Week 12, Week 13 to Week 24, Week 25 to Week 36, and Week 37 to Week 48.

The totality of transfusion burden reduction was evaluated using 24 weeks baseline (sum of 12 weeks historical data and 12 weeks run in data). Baseline of 48 weeks transfusion burden was defined as 2 times 24 weeks baseline transfusion burden. Descriptive statistics (n, mean, median, SD, range) for totality of transfusion burden reduction along with the change from baseline were summarized for each treatment group by 24 weeks and 48 weeks. Only subjects whose efficacy cutoff date was on or beyond end of the week 24/48 interval were included in the analysis.

A waterfall plot was provided for the 24-week post-baseline transfusion burden percent change from baseline by treatment group and time point. Individual subject's transfusion burden percent change from baseline was displayed in a single bar.

No further analysis for key secondary efficacy endpoints will be included in the final CSR.

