10.7 Missing Data Imputation

In case of any missing data for RBC transfusion units records and MRI liver iron content, imputation will be applied for each section.

The imputation for RBC transfusion units is stated in Section 10: if at the time of data summary, a subject's efficacy cutoff date is before the end of the 12-week interval or a subject has any invalid transfusion records (i.e., transfusion unit not available) during the specified 12 week interval, this subject will be included in the analysis as a non-responder.

The imputation logic for missing LIC value is stated in Section 10.5.2: the value of LIC will be either the value collected from eCRF or the value derived from T2*, R2* or R2 parameters depending on which techniques and software were used for MRI LIC data acquisition.

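### The last dose + 20 efficacy cutoff falls one day short of the end of Week 37-48, so on-schedule completers can be scored as non-responders by rule, and it conflicts with protocol 9.6.1

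*SAP*

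**What the plan says.** **The cutoff.** In SAP section 10, the cutoff applied in the first report's analyses "was defined as the minimum date among death date, study discontinuation date, last dose date + 20, and 11MAY2018". Transfusion records are used only up to that date. For the primary and key secondary endpoints, a subject whose cutoff comes before the end of the 12-week interval is scored as a non-responder. SAP 10.7 repeats the rule: "this subject will be included in the analysis as a non-responder". Neither section makes an exception for subjects who completed 48 weeks.

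**The interval.** SAP 5.1 assigns Day 1 to baseline, so every efficacy window is shifted by one day: "Week 37 - 48 interval: from Day 254 to Day 337". SAP 10.3 applies the same cutoff to the descriptive total-burden summary: "Only subjects whose efficacy cutoff date was on or beyond end of the week 24/48 interval were included in the analysis".

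**Leaving treatment at Week 48.** Continuing after Week 48 is optional. Under protocol Figure 4, footnote d, a completer who does not go on to long-term treatment moves to post-treatment follow-up.

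**Transfusion recording.** The transfusion rows of protocol Table 3 read "Record on ongoing basis, until 9 weeks Post-last Dose". For early discontinuers, footnote 24 extends this: data are "reported up to 48 weeks Post Dose 1 Day 1 or Week 9 post last dose whichever is the later date".

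**Use of the records.** Protocol 9.6.1, having said that records of early discontinued subjects are still collected to 48 weeks, states: "All the transfusion records will be used to evaluate primary and secondary endpoints".

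**The concern.** There are two related problems.

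- **A one-day gap for completers.** Last dose + 20 is the last day of a 21-day cycle counted from the dose day. The efficacy windows end one day later, because they start on Day 2. A completer on the exact schedule who does not continue is then failed on the Week 37-48 endpoints although the whole interval lies inside the planned recording period. What decides the outcome is the date of the last dose, not whether transfusions were observed.
- **A conflict over early discontinuers.** The protocol keeps collecting their transfusions so that these can be used. The SAP describes the same collection and then overrides the records with non-response on every responder endpoint, including the primary.

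Key secondary endpoints 1 (at least 33%, Week 37-48) and 3 (at least 50%, Week 37-48) are in the gatekeeping sequence, and endpoint 1 gates endpoints 2 and 3. Misclassification there carries down the testing order.

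**Working it through.** **Inputs.** Efficacy windows (SAP 5.1); cutoff and non-responder rule (SAP 10); Day 1 = first dose (SAP 18.2); dosing every 21 days (protocol 6.2); visit window of ±3 days for Dose 2 onward, and Dose 17 at Week 49 in the Long-term Treatment Period (protocol Table 3); recording to 9 weeks after last dose (protocol Table 3); 200:100 subjects, 40% versus 20%, two-sided 0.05, 10% drop-out, 90% power (protocol 9.3).

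**1. The plan's own figures reproduce.** Week 37-48: 337 - 254 + 1 = 84 days. Week 13-24: 169 - 86 + 1 = 84 days. The sample size also reproduces: the two-proportion formula with continuity correction gives 179 + 90 = 269, and 269/0.9 rounds up to 299 against the stated 300.

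**2. Day of the last dose.** On schedule, dose k falls on Day 1 + 21(k - 1). Dose 16 is Day 316 and Dose 17 is Day 337.

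**3. Cutoff against interval end.** 316 + 20 = 336 < 337, so the subject is a non-responder. The earliest last dose that passes is 337 - 20 = Day 317.

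**4. Sensitivity to the visit window (Dose 16 on Days 313-319).**

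| Dose 16 on Day | Last dose + 20 | Result | Last dose + 21 | Result |
|---|---|---|---|---|
| 313-315 | 333-335 | fails | 334-336 | fails |
| 316 | 336 | fails | 337 | passes |
| 317-319 | 337-339 | passes | 338-340 | passes |

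This shows how the rule behaves inside the permitted window. It does not show how often each day occurs.

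**5. Is the interval observed?** Recording runs to 316 + 63 = Day 379, which is 42 days past Day 337. It reaches Day 337 for any last dose on or after 337 - 63 = Day 274.

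**6. Week 13-24.** For the completer above, 336 is past 169, so the primary endpoint and key secondary endpoint 2 are unaffected. The rule bites for a subject whose last dose is on or before Day 148, since 148 + 20 = 168 < 169. On schedule that dose is Dose 8 (1 + 21 × 7 = 148); a delayed Dose 7 on that day fails too.

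**7. Early discontinuers.** Take a last dose on Day 148. The cutoff is Day 168. Under footnote 24, recording runs to the later of 148 + 63 = Day 211 and 48 weeks after first dose, 1 + 336 = Day 337. Everything from Day 169 to Day 337 is collected but unused, and the subject fails the primary endpoint with 83 of its 84 days (Days 86-168) before the cutoff.

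**8. Size.** Each responder recoded lowers the luspatercept rate by 1/200 = 0.5 points (difference -0.5) or the placebo rate by 1/100 = 1.0 point (difference +1.0). The share of responders recoded, f, is not in the documents. As an illustration, assume that the 40%/20% planning rates hold for endpoint 1 and that f is equal in both arms. The difference becomes 20(1 - f) points. Power at 200:100, without continuity correction, is Φ[(d - 1.96·SE0)/SE1], where d is the difference, SE0 the pooled and SE1 the unpooled standard error:

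| f in both arms | Rates | Difference (points) | Power |
|---|---|---|---|
| 0% | 40% v 20% | 20 | 95.0% |
| 5% | 38% v 19% | 19 | 93.4% |
| 10% | 36% v 18% | 18 | 91.4% |
| 20% | 32% v 16% | 16 | 86.3% |
| 30% | 28% v 14% | 14 | 79.3% |

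Unequal shares change the picture. With 20% of luspatercept and 10% of placebo responders recoded, the difference is 32 - 18 = 14 points (power 74.3%). With 10% and 20% it is 36 - 16 = 20 points (power 96.5%).

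**The case against.** - **Delegation to the SAP.** Protocol 9.2 leaves more than missing-data methods to the SAP. It also delegates predefined rules for including or excluding subjects who have data, and names time windows as an example. SAP 10 states its cutoff openly, and SAP 9.1 uses the same + 20 convention for treatment duration. This could be read as a disclosed on-treatment choice. It is a fair point, but a general delegation does not cancel the specific statement in protocol 9.6.1 that all the transfusion records are used. At the least, the two texts need reconciling.
- **A small group.** The affected completer must have a last dose on or before Day 316, must not continue into long-term treatment and must otherwise be a responder. A subject who keeps dosing every 21 days with any net delay has a last in-period dose on Day 317 or later and passes. This stands: the number may be small or even zero, and the seven window days are not a frequency. A subject whose final dose is held and who then stops does fail, however, and by more than one day.
- **The operative rule is elsewhere.** The SAP for the primary CSR was signed on 19JUN2018 and is not among the documents. The present SAP recaps it. This limits certainty about how individual subjects were classified. It does not alter what the text in hand says.
- **The tests are complete.** No pending decision depends on the rule, and the SAP plans no further primary or key secondary analysis. That is a reason to leave the results alone, but not to leave the discrepancy unexplained.
- **The remedy is wider than the gap.** Re-deriving Week 13-24 is not needed for the completer. It is needed for the conflict with protocol 9.6.1, which reaches the primary endpoint.

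**Conclusion.** The point holds. As written, SAP 10 and 10.7 fail a 48-week completer on key secondary endpoints 1 and 3 when the last dose is on or before Day 316 and long-term treatment is not taken up. On the exact schedule the shortfall is one day (336 against 337). The 48-week total-burden summary also excludes this subject. Separately, the cutoff discards collected post-discontinuation records that protocol 9.6.1 says will be used, and this affects all responder endpoints.

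The total effect cannot be sized because the documents give no count. It is 0.5 or 1.0 point per recoded responder, depending on arm. Recoding the same proportion of responders in both arms shrinks the difference by that proportion; unequal recoding can bias it either way.

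The conclusion assumes that last dose means the last dose in any study period, so that subjects who received Dose 17 on or after its scheduled day and before the data cut are unaffected, and that transfusions were recorded as protocol Table 3 plans. Nothing here suggests that the rule was changed after results were seen: the SAP states that the primary analysis plan was signed before database lock.

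**What to change.** Leave the completed results, and the rule that produced them, as reported. Then:

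1. Add to the final CSR a sensitivity analysis, clearly labelled post hoc, that re-derives response at Week 13-24 and Week 37-48 (33% and 50% criteria) from all collected transfusion records.
2. End each subject's observation at the earliest of death, study discontinuation, the end of available transfusion recording under protocol Table 3 and footnote 24, and the data cut. Do not use last dose + 20. Last dose + 21 is not enough, since Dose 16 on Days 313-315 would still fail. Do not use the date of the last transfusion either, because a transfusion-free subject would then fail.
3. Report the number reclassified in each arm, split into 48-week completers and early discontinuers.
4. State in SAP 10 and 10.7 that the completed analyses departed from protocol 9.6.1, and amend the SAP 10.2 and 10.3 statements that no further primary or key secondary analysis is planned.

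The cost is one rerun on locked data, one extra table and a short SAP note. No new data are needed. The drawback is that the result carries a post hoc label.
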